- Complete the (SUS) after they have finished using the App (Appendix 1.5). Participate in a Follow Up interview (Appendix 1.6) which will assess the youth's experience with their recovery using The Back2Play App, ask about any other interventions they had and if they have experienced a repeat injury during the time in the study.
- Delete the App from their phone during this interview and arrange to return (by scheduled pick up or FedEx label sent by The Research Assistant) device(s).
- 3 months following study enrollment, participants will be sent a survey through REDCap about reinjury to complete.

Participants who have been randomized to the usual care group will be asked to:

- Receive the usual course of care given by the hospital, General Practitioner or clinic which may or may not include written guidelines, suggestions or resources
- Complete the initial post-concussive symptom survey with The Research Assistant.
- Complete symptom surveys and daily surveys about cognitive and physical activities as well as self-rating of participants' own cognitive level of activity and stage of concussion recovery every 24 hours emailed by REDCap until 2 days following symptom resolution.
- Participate in a Zoom visit 2 days after symptom resolution or after 3 months of
 participation for those who do not achieve symptom resolution. Participants will
 be asked questions regarding their knowledge of and ability to follow the Usual
 Care guidelines they received and about any other interventions they may have
 received. This Zoom visit will be recorded and saved to a secure, password
 encrypted study computer.
- 3 months following study enrollment, participants will be asked to complete a survey about reinjury.

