8. DESIGN

Phase 3 of this study has both quantitative and qualitative components. The aims of the qualitative components of the study are to determine if participants liked using The App, and if their experiences of using it helped their recovery from concussion. In addition, qualitative data will be used to review any improvement suggestions to The App before commercialization. Using both qualitative and quantitative research methods we will explore

the usability of The Back2Play App components under consideration for the final version of the App to be commercialized.

Primary Research Outcomes

To assess:

- Risk for repeat head injuries within three months of study completion (3-6 months after injury)
- Duration of symptoms: Time to symptom resolution from date of injury

Secondary Research Outcomes

To assess:

- 1) The frequency of symptoms using PCSS.
- 2) Time to return to activity and time to progress through the 6 stages of RTA
- 3) Perceptions of the platform by parents and youth.
- 4) Accuracy of the algorithm embedded in the background of The App classifying the participant's stage of recovery

Measures

Symptoms

Concussion symptoms will be assessed on The Back2Play App for those randomized to The App group and via REDCap for those randomized to Usual Care. A modified version of the PCSS (consisting of 22 symptoms) will be completed by youth in both groups. The Likert scale was modified to detect the presence of symptoms rather than symptom severity. Symptom data will be collected 3x/day for participants using The Back2Play App and every 24 hours for participants in the Usual Care group.

Cognitive Activity

Cognitive activity will be assessed using a modified version of the scale developed by Brown et al. Participants in both groups will be asked to complete this scale once per day through REDCAP which will appear as follows:

"Please rate 1-5 what you've been doing today"

- 1- None- No reading, homework, text messaging or screen time (T.V., cell phone), can talk on phone
- 2- Minimal- 15 minutes of screen time or schoolwork 2x daily. Socialize with 1-2 friends, no longer than 30 minutes,
- 3- Moderate- Homework in 15 minutes blocks for a maximum of 45 minutes. Screen time/T. V in 15-minute blocks, for up to an hour daily.
- 4- High- Complete as much homework as tolerated. 1 test/week or tests with accommodation (i.e. longer time to write), less reading, homework and screen time than normal
- 5- Full- no restrictions to cognitive activity

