
Cognitive and Physical Activities

Engagement in cognitive and physical activities will be measured once per day in those using the App as well as for those in the Usual Care group. The activities surveyed will match those recommended for each stage of RTA/RTS (Appendix 1.2)

Time to Stage

Participants in both groups will report their stage of RTA/RTS. The time from injury to each stage will be used to determine the time to stage and completion of the RTA/RTS guidelines.

Rate of Reinjury

All participants be asked at study completion and 3 months after symptom resolution if they have hit their head again in such a way that they experienced symptom exacerbation or return of symptoms for more than one day, if they moved back a stage in the guidelines for recovery, or if they sought medical care from hitting their head since the initial injury.

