Appendix 1.1 Business Rules for In-App Notifications

Progression through the CanChild RTA/RTS Guideline

- 1. Participants cannot enter RTA Stage 4 until they have completed RTS Stage 1-3
 - o If the participant reports RTA Stage 4 when they are in RTS Stage 1 or 2 they will receive the message "Stage 1, 2 and 3 come before RTA Stage 4!"
- 2. Participants must complete RTS Stage 5 (Full Return to School) before they can enter RTA Stage 4.
 - If the participant reports RTA Stage 4 or 5 when they are in RTS Stage 3 through 5, they will receive the message "You should complete RTS Stage 4-5 before RTA Stage 4-6".
- 3. Participants will be recommended to move to Stage 2 of RTS after 7 days
 - o If the participant reports RTS Stage 1 for 7 days, they will receive the message "You reported being in Stage 1 for 1 week, time to move to Stage 2!"
- 4. Participants will be recommended to move to Stage 3 of RTS after 14 days
 - o If the participant reports RTS Stage 2 for 14 days, they will receive the message "You reported being in Stage 2 for 2 weeks, time to move to Stage 3!"
- 5. Once in RTS Stage 3, participants cannot move back to Stage 2.
 - o If the participant reports RTS Stage 3 and moves back to RTS Stage 2, they will receive the message "Once your reach RTS Stage 3, you should not return to RTS Stage 2".

- 6. Participants are recommended to complete RTA and RTS Stage 1-3 together.
 - o If the participant reports RTA Stage 3 while in RTS Stage 1 or 2, they will receive the message "Remember, RTS and RTA Stage 1 to 3 should go together!"
- 7. Participants will be cautioned when they try and skip a stage
 - o If the participant skips from RTS Stage 2 to RTS Stage 4, they will receive the message "You forgot RTS Stage 3, we recommend you log this stage first!"
- 8. Participants will be cautioned when they try to move back a stage.
 - o If the participant moves back a Stage i.e., RTS Stage 5 to Stage 4, RTA 5 to Stage 4 they will receive the message "*Are you sure you want to move back a stage?*"
- 9. Participants cannot progress to a new stage of RTA/RTS if 2 or more symptoms worsen
 - o If the participant reports that 2 or more symptoms worsen (from morning to evening survey), **and** the participant attempts to progress to a new stage, they will receive the message "We recommend you do not progress to a new stage and inform a parent of your symptoms".

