Appendix 1.6

Follow Up Interview

Ask Everyone:

Tell me about where you are in recovery from your concussion.

Prompts:

Are you still experiencing any symptoms?

Did you hit your head again during your recovery?

If yes did it increase symptoms and how did it affect your recovery?

Are you back fully to school and sport?

Do you feel back to your previous self?

Are there any other therapies or treatments that you tried during your recovery from concussion? Prompts:

Medications, physio, chiro, other medical professionals

Ask App users:

Tell me about your experience in using the App during your recovery from concussion.

Follow Up questions:

Did you receive notifications from the App-give me some examples

Did you do the surveys on your watch or phone?

Did you ever use data or mostly Wi-Fi?

Did you ever forget to charge the watch? How often?

Did you agree with the guidance you were given re: activity or stage levels? (%)

Did you find the App helpful at all in your recovery-how so?

Did you like the App?

Follow up questions:

What were the best features of the App

Were there features you didn't use that much

Were there things that you didn't like or found annoying

How could we make it better?

Ask Usual care group

What was involved in your care and follow up with your concussion?

Were you given some sort of guidelines to follow to return to play and school?

What format were they in?

Did you seek extra treatment or help?

Did you feel you understood how to get better and get back to activities and school after your concussion?

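### Time to return to activity is read from self-reported guideline stage, which App messages act on and Usual Care youth may not share, so it can differ between arms without a difference in recovery

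*Combined protocol and SAP*

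**What the plan says.** Section 8 (Secondary Research Outcomes) lists "Time to return to activity and time to progress through the 6 stages of RTA". The introductory Research Question also asks about return to full activity. The measure is given in Section 8 under Time to Stage: "Participants in both groups will report their stage of RTA/RTS", and "The time from injury to each stage will be used to determine the time to stage and completion of the RTA/RTS guidelines". No assessor is described, and Section 6 states that neither participants nor researchers can be blinded.

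In the App arm, Appendix 1.1 sets messages that respond to the reported stage. Rule 3 reads "Participants will be recommended to move to Stage 2 of RTS after 7 days" and rule 4 reads "Participants will be recommended to move to Stage 3 of RTS after 14 days". Rule 6 reads "Participants are recommended to complete RTA and RTS Stage 1-3 together". Rules 5, 7 and 8 query moving back or skipping, rules 9 and 10 advise against progressing when symptoms worsen or increase, and rules 11 to 13 give minimum times per stage by symptom stratum.

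In Usual Care, Section 7 says that youth often receive whatever gradual-return guideline their practice uses, and then describes care "which may or may not include written guidelines, suggestions or resources". These youth still rate their stage every 24 hours.

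In both arms daily reporting ends two days after symptoms resolve (Section 7). Section 9.5 names no analysis for time to return to activity.

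**The concern.** An outcome that compares arms should be measured on the same scale in each, and the treatment should not alter the reading except through the thing being measured. Reported stage falls short on both counts. In one arm the App comments on the report itself. In the other, a youth may be asked for a stage number from a scheme never supplied, or may answer with a different scheme in mind.

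At stake is the reading of a result on return to activity. A shorter time to stage in the App arm might mean earlier recovery, better adherence, or only a different habit of reporting. A longer time, or no difference, would be equally hard to read. A second problem is that the stage data may end before full return takes place.

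**Working it through.** The plan gives no figure for this outcome to reproduce. The sample size (128 / (1 − 0.20) = 160) concerns repeat injury and is not affected. The check is therefore mainly one of setting the texts side by side.

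**1. What acts on the reported stage, by arm**

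| Appendix 1.1 rule (App arm only) | Scale | Likely effect on reported time |
|---|---|---|
| 3: prompt after 7 days in Stage 1 | RTS | shorter |
| 4: prompt after 14 days in Stage 2 | RTS | shorter |
| 1, 2, 6: RTA not to run ahead of RTS | RTA | longer |
| 7: query a skipped stage | RTS in its example | longer |
| 5, 8: query a move back | RTS (5); both (8) | later stage kept on record |
| 9, 10: do not progress with worse or more symptoms | both | longer |
| 11–13: minimum 24 hours, 48 hours or 1 week per stage | both | longer |

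Usual Care has none of these messages and no assured stage definitions. Because the rules pull both ways, the net direction is unknown.

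**2. What can be said about size**

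Rules 3 and 4 together span 7 + 14 = 21 days of reported RTS Stages 1 and 2. To see whether such prompts could matter at all, assume equal true recovery in the two arms, exponential times in each stage with medians M1 and M2, and a share c of App youth who report the next stage when prompted. None of these inputs is in the documents. With mean m = M / ln 2, the mean time saved is c × [m1 × 2^(−7/M1) + m2 × 2^(−14/M2)].

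- Medians 3 and 7 days: m1 = 4.33, m2 = 10.10, total 14.43. Saved at c = 1: 4.33 × 0.198 + 10.10 × 0.25 = 0.86 + 2.52 = 3.38 days, or 23%. At c = 0.25: about 6%.
- Medians 7 and 14 days: m1 = 10.10, m2 = 20.20, total 30.30. Saved at c = 1: 5.05 + 10.10 = 15.15 days, or 50%. At c = 0.25: 12.5%.

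So the mean reported time to RTS Stage 3 could fall by about 6% to 50% through reporting alone. This leaves out the holding-back messages, concerns RTS Stage 3 only, and is not an estimate for return to full activity.

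**3. Whether the stage data reach full return**

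- Section 2 says the protocols do not allow strenuous activity or contact sport while symptoms are present. Appendix 1.1 rule 18 places contact at RTA Stage 6.
- Reporting continues for 2 days (48 hours) after resolution. At the App's own minimum times, that leaves room for 48 / 24 = 2 stages in Strata A, 48 / 48 = 1 in Strata B, and 48 / 168 = 0.29, so no complete stage, in Strata C.
- Section 2 gives RTA six stages. The RTA question in the Appendix 1.2 App surveys offers 1 to 5. Section 7 describes the self-rating as 1 to 5 or 6. The Usual Care form is not reproduced, so it is unclear whether Stage 6 can be recorded there.

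**4. What else is collected**

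The interview asks everyone "Are you back fully to school and sport" (Appendix 1.6), but without dates. It takes place two days after resolution, or at 3 months if symptoms persist. Both arms also receive a later reinjury survey, and both complete the daily activity survey and the cognitive activity scale (Section 8).

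**The case against.** A reader might infer that the App moves youth through the RTA stages by calendar, to a fixed point at 21 days whatever their recovery. The documents do not support that. Rules 3 and 4 concern RTS only. Rule 6's message appears only when a youth reports RTA Stage 3 while in RTS Stage 1 or 2, so it restrains RTA. Rules 9 and 10 and the stratum messages depend on symptoms. Nor do the documents show that the arms will differ, or in which direction.

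It is also fair to say that changing how youth progress is what the App is for: the hypothesis is that adherence speeds return to activity and school. Only a change in reporting without a change in behaviour is artefact. That stands, but reported stage cannot separate the two, and the research question asks about recovery.

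Both arms are asked for a stage daily and given activity lists matched to the stages. This standardises when and what youth are asked. It does not standardise what a stage means to a youth without the guideline.

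Finally, this is a secondary outcome in a trial described as a feasibility RCT. That limits the weight of the point but does not remove it, because return to full activity is named in the research question.

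**Conclusion.** The concern holds in a limited form. Time to return to activity rests only on unblinded, self-reported stage. App messages act on that report in one arm, and a common set of stage definitions is not assured in the other. Time to stage can therefore differ between arms without a difference in recovery, and the analysis plan does not deal with this. Direction and size cannot be derived; the 6% to 50% range above rests wholly on assumed inputs and applies to RTS Stage 3.

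Separately, full return will often go unrecorded, because reporting stops two days after resolution and the App survey has no RTA Stage 6. How often depends on the stage youth have reached when symptoms resolve, which the documents do not give. The point is worth correcting, but it does not undermine the trial's design.

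**What to change.** Define the outcome as time from injury to the date of full return to sport and, separately, to the date of full return to school, asked in identical words in both arms.

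- Add the two date fields to the existing 3-month survey, with a not-yet option censored at the survey date. Sections 7 and 8 count the three months from different starting points (enrolment and symptom resolution); settle this so that follow-up is the same in both arms.
- Add the same fields to the existing interview question, for youth already back by then. The interview alone is often too early for return to sport.
- Name the analysis in Section 9.5. The survival methods already planned for symptom resolution would serve.
- Report stage times as descriptive, and reconcile the App's RTA options with the six stages. The alternative is to show the same stage definitions beside the daily question in both arms, but only if the sponsor accepts that this gives Usual Care guideline content.
- Use the daily activity surveys and the cognitive activity scale as a supporting check. They are collected daily in both arms, so they avoid long recall.

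The cost is two date fields on instruments that both arms already complete. The dates will be recalled and unblinded, and App advice may still influence when youth actually return, which is part of its intended effect.

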8. DESIGN

Phase 3 of this study has both quantitative and qualitative components. The aims of the qualitative components of the study are to determine if participants liked using The App, and if their experiences of using it helped their recovery from concussion. In addition, qualitative data will be used to review any improvement suggestions to The App before commercialization. Using both qualitative and quantitative research methods we will explore

the usability of The Back2Play App components under consideration for the final version of the App to be commercialized.

Primary Research Outcomes

To assess:

- Risk for repeat head injuries within three months of study completion (3-6 months after injury)
- Duration of symptoms: Time to symptom resolution from date of injury

Secondary Research Outcomes

To assess:

- 1) The frequency of symptoms using PCSS.
- 2) Time to return to activity and time to progress through the 6 stages of RTA
- 3) Perceptions of the platform by parents and youth.
- 4) Accuracy of the algorithm embedded in the background of The App classifying the participant's stage of recovery

Measures

Symptoms

Concussion symptoms will be assessed on The Back2Play App for those randomized to The App group and via REDCap for those randomized to Usual Care. A modified version of the PCSS (consisting of 22 symptoms) will be completed by youth in both groups. The Likert scale was modified to detect the presence of symptoms rather than symptom severity. Symptom data will be collected 3x/day for participants using The Back2Play App and every 24 hours for participants in the Usual Care group.

Cognitive Activity

Cognitive activity will be assessed using a modified version of the scale developed by Brown et al. Participants in both groups will be asked to complete this scale once per day through REDCAP which will appear as follows:

"Please rate 1-5 what you've been doing today"

- 1- None- No reading, homework, text messaging or screen time (T.V., cell phone), can talk on phone
- 2- Minimal- 15 minutes of screen time or schoolwork 2x daily. Socialize with 1-2 friends, no longer than 30 minutes,
- 3- Moderate- Homework in 15 minutes blocks for a maximum of 45 minutes. Screen time/T. V in 15-minute blocks, for up to an hour daily.
- 4- High- Complete as much homework as tolerated. 1 test/week or tests with accommodation (i.e. longer time to write), less reading, homework and screen time than normal
- 5- Full- no restrictions to cognitive activity

Cognitive and Physical Activities

Engagement in cognitive and physical activities will be measured once per day in those using the App as well as for those in the Usual Care group. The activities surveyed will match those recommended for each stage of RTA/RTS (Appendix 1.2)

Time to Stage

Participants in both groups will report their stage of RTA/RTS. The time from injury to each stage will be used to determine the time to stage and completion of the RTA/RTS guidelines.

Rate of Reinjury

All participants be asked at study completion and 3 months after symptom resolution if they have hit their head again in such a way that they experienced symptom exacerbation or return of symptoms for more than one day, if they moved back a stage in the guidelines for recovery, or if they sought medical care from hitting their head since the initial injury.

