3. METHODS

Description of Population and Sample

Our population consists of male and female youth aged 10-18 years that have been diagnosed with a concussion by a physician. Youth presenting to the David Braley Clinic, McMaster Children's Hospital, HWCDSB, Montreal Children's Hospital or physicians in the community will be randomly assigned to the intervention or control groups.

A clinically significant effect of 10% decrease in repeat head injury and 10% decrease in recovery time would be of interest. The sample size calculation was done using parameters with a two sided significance of 0.05 and a power of 0.8 and based on our primary outcome of repeat head injury which is a binomial variable. Our anticipated incidence rate was compared to two rates of incidence in clinical settings and in the literature:

- 16% rate common in the literature
- our anticipated 2% rate with adherence to protocols (from previous B2P study) N=128
- 37% rate from concussion clinic at MCH and
- 13% rate of our pilot data N=100.

The larger number will be sought (sample size takes into consideration 20% refusal rate and loss to follow up) therefore we will recruit N=160. With an average of 25-30 new cases per month from the sources outlined above, 60% consent rate, and 12 months recruitment, it is feasible to attain this sample of youth.

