9.5. DATA ANALYSIS PLAN

The recordings of online consent (Zoom), for Phase 3, will be stored on a study computer and saved to a secure password encrypted server. As described above, participants will be asked to complete the (SUS). The SUS yields a single number representing a composite measure of the overall usability of the system being studied. Adjustments and modifications to The Back2Play App will be made before commercializing the product.

We will collect and report descriptively all demographic information, injury-related data (type, mechanism of injury, numbers of injuries), youth premorbid health history. Descriptive statistics such as means, medians, and frequencies will be reported where appropriate. Baseline comparisons will be performed between those that use The App and those whose recovery involved Usual Care with variables of mechanism of injury, age, sex, school performance and concussion history. These variables will be-analyzed using Pearson Chi Squared Cross Tabulations, T-Test and ANCOVA, to ensure the groups are similar. We will also evaluate agreement of the algorithm with the self-reported stage of recovery participants input using these same statistics.

The dichotomous variable, repeat injuries (coded as yes or no), will be analyzed using multivariate logistic regression and resulting odds ratios to determine if using The Back2Play App decreases risk of repeat injury. Confounders of age, gender, number of symptoms, time since last injury and comorbidities of premorbid mental health issues or learning disabilities will be examined as to their potential impact on outcomes. Many of these variables will be correlated with each other and these correlations will need to be examined carefully before they are entered into the analyses.

Time to symptom resolution will be analyzed using survival curves with Multivariate Cox regression analysis. Cox regression (also called proportional hazard models) is a method of survival analysis that models the time until some event as a function of either continuous or categorical predictors, allowing for the fact that not all subjects will experience the events of interest and that they will occur at different times.

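### Two primary outcomes but only one is sized, and no rule says which result makes the trial positive or how the error rate is shared between them

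*Combined protocol and SAP*

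**What the plan says.** - **Outcomes.** Section 8 (Primary Research Outcomes) lists repeat head injury and "Duration of symptoms: Time to symptom resolution from date of injury" as two bullets, with no ranking.
- **Sample size.** Section 3 uses "a two sided significance of 0.05 and a power of 0.8" and says the calculation is "based on our primary outcome of repeat head injury which is a binomial variable", in the singular. It gives two scenarios: 16% v 2% (N=128) and 37% v 13% (N=100). The larger is raised to 160 for 20% refusal and loss. Section 3 also names a reduction in recovery time as being of interest, but gives no power calculation for it.
- **Analysis.** In section 9.5 repeat injury "will be analyzed using multivariate logistic regression and resulting odds ratios to determine if using The Back2Play App decreases risk of repeat injury". Separately, "Time to symptom resolution will be analyzed using survival curves with Multivariate Cox regression analysis". Neither sentence gives a significance level.
- **Decision rule.** No hierarchy, alpha split, co-primary requirement or success criterion appears anywhere in the document. The outcome list, the sizing paragraph and the analysis section are all present in the text, so this is not a gap left by redaction or PDF extraction.

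**The concern.** Section 3 treats repeat head injury as the single primary outcome; section 8 gives it an equal partner. Section 9.5 presents the logistic model as enough to decide whether the App lowers reinjury risk, so that result could support a claim by itself. Nothing stops the Cox result from doing the same.

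Section 6 states that participants and researchers are not blinded. Without a rule fixed beforehand, either outcome could be put forward as the trial's answer once results are known. The only significance level in the document, 0.05, would then not be the error rate of the trial's conclusion, and the stated 80% power would describe only one of the two routes to a claim.

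**Working it through.** **Inputs.** From section 3: two-sided alpha 0.05, power 0.80, 16% v 2% with N=128, 37% v 13% with N=100, 20% refusal and loss, target 160. From section 6: equal allocation (50%). The document gives no correlation between the two outcomes, so a range is shown.

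**1. The plan's own sample size.** For two proportions with pooled variance and no continuity correction:

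n per arm = [z(1−α/2)·√(2·p̄·q̄) + z(0.80)·√(p1·q1 + p2·q2)]² / (p1 − p2)²

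- 16% v 2%: p̄ = 0.09, √0.1638 = 0.4047, √0.1540 = 0.3924. n = (1.960 × 0.4047 + 0.842 × 0.3924)² / 0.14² = 64.4. Rounded up this is 65 per arm, 130 in total; the stated 128 is 64 per arm.
- 37% v 13%: p̄ = 0.25, √0.3750 = 0.6124, √0.3462 = 0.5884. n = (1.960 × 0.6124 + 0.842 × 0.5884)² / 0.24² = 49.9, so 50 per arm and 100 in total, as stated.
- Inflation: 128 / (1 − 0.20) = 160, as stated.

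The design therefore reproduces as one test of repeat head injury with the whole 0.05 spent on it.

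**2. Error rate if each outcome is tested at 0.05 and either suffices.**

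- Independent tests, either direction: 1 − 0.95² = 0.0975.
- Independent tests, App's favour only: 1 − 0.975² = 0.0494, against 0.025 for one test.
- Correlated test statistics (bivariate normal, critical value 1.96):

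| Correlation | Any false significant result | False result in the App's favour |
|---|---|---|
| 0 | 0.0975 | 0.0494 |
| 0.3 | 0.0951 | 0.0476 |
| 0.5 | 0.0907 | 0.0454 |
| 0.7 | 0.0835 | 0.0417 |
| 0.9 | 0.0704 | 0.0352 |
| 0.999 | 0.0521 | 0.0260 |

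**3. Error rate if both outcomes must be significant.** It cannot exceed 0.05, because a false claim then requires a false result on a test held at 0.05. The cost moves to power: the chance of winning on both cannot exceed the smaller of the two powers, and only one of them is given.

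**4. Power for repeat head injury at 0.025,** the level that applies under Holm when time to resolution does not succeed. With 64 per arm (128 evaluable), power = Φ{[(p1 − p2)·√n − z(1−α/2)·√(2·p̄·q̄)] / √(p1·q1 + p2·q2)}.

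- 16% v 2% at 0.05: Φ[(1.120 − 0.793) / 0.3924] = 0.797.
- 16% v 2% at 0.025 (critical value 2.241): Φ[(1.120 − 0.907) / 0.3924] = 0.706.
- 37% v 13% at 0.025: Φ[(1.920 − 1.373) / 0.5884] = 0.824.

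Holding 80% power at 0.025 for 16% v 2% takes 79 per arm: 158 evaluable, and 158 / 0.80 = 197.5, so 198 recruited. For 37% v 13% it takes 122 evaluable, and 122 / 0.80 = 152.5, so 153 recruited, which is within the planned 160.

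**The case against.** A reader might infer that the plan tests both outcomes at two-sided 0.05, and that the chance of a false claim for the App is therefore nearly twice 0.05. The document does not support that, for four reasons.

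- **The level.** The 0.05 appears once, as an input to the sample size for repeat injury. Section 9.5 sets no level for either model. That both would be tested at 0.05 is the natural default, but it is an inference.
- **The success rule.** Nothing says that either outcome is enough. The Research Question joins its aims with 'and', and if both primaries had to succeed the error would not exceed 0.05. This stands as a possibility, but not as a rule: the same sentence also includes return to full activity, which section 8 makes secondary, so it cannot be read as a co-primary requirement.
- **Direction.** The 9.75% includes false results against the App. For false results in its favour the like-for-like comparison is about 4.9% with 2.5%.
- **Independence.** This is the unfavourable end of the range. Section 8 (Rate of Reinjury) counts worsening or return of symptoms after a new head impact as reinjury, so the two outcomes are plausibly linked. The effect is modest, though: the either-direction rate stays above 9% up to a correlation of 0.5.

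It can also be said that the Hypothesis text labels this phase a feasibility RCT, for which strict error control matters less. That mitigates but does not settle the point: the description of Phase 3 sets a goal of comparing effectiveness with usual care, and section 3 powers a hypothesis test at 80%.

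These objections limit what can be said about size. They leave untouched the mismatch between sections 3 and 8 and the absence of any decision rule.

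**Conclusion.** The point holds in conditional form. Two primary outcomes are declared, one is sized, each has its own model, and no hierarchy, alpha split or success rule connects them.

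If each were tested at two-sided 0.05 and either sufficed, the family-wise error in either direction would be up to 9.75% (independence), about 9.1% at a correlation of 0.5, and close to 5% at full correlation. In the App's favour it would be up to about 4.9% against 2.5%, taking the correlation as zero or positive. These figures rest on an assumed test level, an assumed either-outcome rule and an unknown correlation. They should not be quoted as the plan's error rate, because the plan does not define one.

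The change should be made before results are seen. The conflict between sections 3 and 8 needs resolving whichever error rate is assumed.

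**What to change.** Make sections 3 and 8 agree on the status of each outcome, and add the decision rule to section 9.5.

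**Preferred: a fixed sequence.** Test repeat head injury, the sized outcome, at two-sided 0.05. Test time to symptom resolution at two-sided 0.05 only if repeat head injury is significant. This holds the family-wise error at 0.05, keeps the stated power for repeat injury, needs no extra patients and takes a sentence or two. The cost is that a favourable result on time to resolution cannot be claimed if repeat injury fails.

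**Alternative: Holm.** Compare the smaller p-value with 0.025 and, only if that succeeds, the other with 0.05. Either outcome can then carry the claim. Restate worst-case power for repeat injury at 128 evaluable: about 71% for 16% v 2% (a loss of about 9 points from 80%) and about 82% for 37% v 13%. Guaranteeing 80% in the 16% v 2% scenario would take 158 evaluable, or 198 recruited, instead of 160.

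Under either option, state the power for time to symptom resolution, which the document does not give.
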